7.1. Subgroup analyses

We will conduct a prespecified subgroup analysis to assess the incidence of Ng plus Ct in screening vs. non-screening arms in participants with lower-risk behavior. An individual with lower-risk behavior is defined a priori as those individuals who report 4 or fewer partners per 3-month period in all 5 relevant 3 month periods with data available. These periods are the 3-months prior to study enrollment as well as the four 3 month periods during study follow up. The analysis will be analogous to the analysis of the primary objective, but restricted to participants with lower-risk behavior.

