5 TRIAL DESIGN

This study is a multi-centre, controlled, randomized trial of 3x3 Ng/Ct screening (comparator) vs. no screening (intervention). It will be performed in the PrEP cohorts situated at the ITM, HSP, CHU, UZG and EH. All men in follow up at these five centres who report having had sex with another man in the previous year and are enrolled for PrEP follow up will be eligible to participate in the study. After signing informed consent participants will be randomized via a computer-generated schema to either 3x3 screening or no Ng/Ct screening (see section 8.3). In both arms, participants will be followed up in an identical fashion including 3x3 screening. The only difference between the arms will be that in the screening arm, Ng/Ct results will be sent by the STI Laboratory to the study physicians and these participants will be treated and partner contact tracing will be done. The STI Laboratory will only process the samples/report the results from the non-screening arm at the end of the study. In both arms, all individuals with symptoms compatible with Ng or Ct will be tested and treated for these infections according to current best practice guidelines. At the end of the 12-month study period, participants whose most recent tests were positive for Ng or Ct will receive treatment for these.

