8.4 Blinding

This study will be unblinded.

Study Participants: The participant will not be explicitly informed to which intervention arm they have been randomized. However it will not be possible to completely blind the participants to which arm they are in, since those in the screening arm who test positive will be recalled for treatment of an asymptomatic infection. In addition, participants will be able to see which arm they are in the 3 weeks after enrolment if they login online to obtain their Ng/Ct results (a service that is in the process of becoming available to all PrEP recipients). If they are in the screening arm they will be able to see either a positive or a negative result for Ng/Ct. If they are in the no-screening arm, no test result will be visible. From this they will be able to deduce which arm they are in.

Doctors and study nurses: The attending doctors will not be blinded. Blinding the attending doctors would be very difficult within this study design as a week after each study visit, the doctors will receive the results of the Ng/Ct screening tests, but only for the participants in the 3x3 screening arm. At this point the doctor will be able to deduce which arm the participant is in. As a result, we have decided that the attending doctors will not be blinded to study arm allocation.

Statistician: The study statistician will be blinded until the statistical analysis plan (SAP) is approved.

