8.7 Trial assessments

These assessments will be performed according to standard of care at each participating centre. In certain centres such as HSP the laboratory tests are performed the week before the clinic visit. These laboratory assessments will be considered to be the laboratory results for that particular visit. Participants in the non-screening arm will not be informed of their results at month 3, 6 and 9. They will only be informed about the result of the sample taken at month 0 and month 12.

Screening/enrolment visit (Day 0):

- Eligibility check
- Informed Consent Procedure
- Demographic and question regarding sexual behaviour
- PrEP questionnaire (only at ITM)
- Ask if symptoms compatible with STI
- Physical examination if symptomatic
- STI history last 12 months
- Antibiotic usage last 6 months
- Randomization
- Collection of results of syphilis and HIV testing (performed according to routine practice)
- Sample collection (according to standard practice of the participating sites.):
 - o Urine sample (first-void) (Ng/Ct NAAT)
 - o Pharyngeal swab (Ng/Ct NAAT)
 - o Anorectal swab (Ng/Ct NAAT)

Visit month 3 (can be between one week earlier and 6 weeks later):

- Ask if symptoms compatible with STI
- Physical examination if symptomatic
- STIs diagnosed since last visit (at study site or outside)
- Antibiotic usage
- Question regarding sexual behaviour
- PrEP questionnaire (only at ITM)
- Collection of results of syphilis and HIV testing (performed according to routine practice)

- Sample collection:
 - o Urine sample (first-void) (Ng/Ct NAAT)
 - o Pharyngeal swab (Ng/Ct NAAT)
 - o Anorectal swab (Ng/Ct NAAT)

Visit month 6 (can be between one week early and 6 weeks late):

- Ask if symptoms compatible with STI
- Physical examination if symptomatic
- STIs diagnosed since last visit (at study site or outside)
- Antibiotic usage
- Question regarding sexual behaviour
- PrEP questionnaire (only at ITM)
- Collection of results of syphilis and HIV testing (performed according to routine practice)
- Sample collection:
 - o Urine sample (first-void) (Ng/Ct NAAT)
 - o Pharyngeal swab (Ng/Ct NAAT)
 - o Anorectal swab (Ng/Ct NAAT)

Visit month 9 (can be between one week early and 6 weeks late):

- Ask if symptoms compatible with STI
- Physical examination if symptomatic
- STIs diagnosed since last visit (at study site or outside)
- Antibiotic usage
- Question regarding sexual behaviour
- PrEP questionnaire (only at ITM)

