11.3.2 Primary outcome analysis

We will analyse the primary outcome both using Intention-to-Treat and Per-Protocol approaches, with Per-Protocol as primary approach. In the Intention-to-Treat analysis, all participants will be analysed according to their randomized allocation, even in case they receive another intervention, show protocol violations prior to or during the study, or are lost-to follow. In the per-protocol analysis only participants who receive intervention as planned, and follow the protocol as planned

are included. If the person urgently requires knowing if they are infected with Ng/Ct or not this will be done by repeat testing for these infections. If this test is positive for Ng/Ct then this will be counted as an intervisit infection in the final analysis. In each arm, the incidence of Ng plus Ct will be estimated together with 95% confidence interval. Estimates will be based on a Poisson regression model with number of diagnoses as dependent variable, arm as independent variable, log(number of visits) as offset and a random intercept for site. This model will also provide an estimate of the log incidence rate ratio (no screening versus screening), together with 95% confidence interval. The 'no screening' arm is proven to be non-inferior if the upper limit of the 95% confidence interval is lower than log(1.25).

Visits with missing data on the diagnosis of Ng or Ct, will be excluded from the calculation of the incidence rate (excluded both from numerator and denominator).

Subgroup analysis:

We will conduct a prespecified sensitivity analysis to assess the incidence of Ng plus Ct in screening vs. non-screening arms ***in participants with lower-risk behavior***. An individual with lower-risk behavior is defined a priori as those individuals who report 4 or fewer partners per 3-month period in all 5 relevant 3 month periods. These periods are the 3-months prior to study enrollment as well as the four 3 month periods during study follow up). The analysis will be analogous to the analysis of the primary objective, but restricted to participants with lower-risk behavior.

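### The lower-risk subgroup is defined mainly by partner counts reported after randomisation in an unblinded trial, so its rate ratio is a randomised comparison only if arm leaves those counts unchanged

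*SAP*

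**What the plan says.** SAP 7.1 admits to the lower-risk subgroup "individuals who report 4 or fewer partners per 3-month period in all 5 relevant 3 month periods with data available". Protocol 11.3.2 uses the same threshold and the same five periods, without the closing qualifier about available data. On timing it states: "These periods are the 3-months prior to study enrollment as well as the four 3 month periods during study follow up". The model is then refitted to that subset: "The analysis will be analogous to the analysis of the primary objective, but restricted to participants with lower-risk behavior".

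On knowledge of allocation, protocol 8.4 declares the study unblinded. Of participants it says "The participant will not be explicitly informed to which intervention arm they have been randomized", but it goes on to describe how online results reveal the arm: "From this they will be able to deduce which arm they are in". Of clinicians it says "we have decided that the attending doctors will not be blinded to study arm allocation".

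The arms also differ in what follows a test. In the screening arm results go to the physicians, and "these participants will be treated and partner contact tracing will be done" (protocol 5). By contrast, "Participants in the non-screening arm will not be informed of their results at month 3, 6 and 9" (protocol 8.7). Symptomatic infections are tested and treated in both arms.

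Protocol 8.6 collects the number of partners in the 3 months before enrolment. Neither document defines a subgroup on that count alone or comments on membership being settled after randomisation.

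**The concern.** Randomisation makes the arms comparable within a subgroup when membership is fixed before allocation. Here it is fixed only at the end of follow-up, from self-reports by people who can work out their arm to clinicians who know it. Setting the threshold in advance does not turn membership into a baseline characteristic.

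There are two routes to trouble. If one arm reports fewer partners than it has, that arm's subgroup takes in people at higher true risk. If one arm really has fewer partners, the rule selects on part of what the policy did and removes it from the comparison.

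A lesser point is the SAP's qualifier about available data. Someone with fewer reported periods has fewer chances to exceed 4, so membership also depends on attendance after randomisation.

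This is the only prespecified subgroup. It is also the trial's only look at the lower-connectivity setting in which protocol 2 thinks individual screening is more likely to help. If the 1.25 rule is carried over, as an analysis modelled on the primary one suggests, a modest shift could change how the subgroup is read.

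**Working it through.** **What the plan supplies.** The documents give no partner distribution and no figure for the subgroup. From protocol 11.1, the mean per visit is 0.79×0.15 + 0.18×0.28 + 0.03×0.34 = 0.1791, and ×4 = 0.716, which agrees with the stated 0.72. A Poisson formula for the log rate ratio with 3.95 visits per person gives a total of 892 against the stated 912. Simulating the plan's own table gives 80.1% power at 912. Then 912/0.90 = 1013.3, rounded up to 1014. The sample size stands, and nothing below bears on it.

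**Timing.** One of the five periods precedes randomisation and four follow it: 4/5 = 80%.

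**Illustration: assumed inputs.** Each person has a partner rate λ, gamma distributed, with mean 4, 6 or 8 per quarter and shape 1 or 2. Quarterly partners X are Poisson(λ). Diagnoses per visit average 0.72/4 = 0.18. The true screening effect is nil. Three risk curves r(X) are used, with c set to give the mean of 0.18:
- steep: 1 − exp(−cX)
- middle: c(1 + X)
- shallow: c√(1 + X)

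**Formula.** Let b(λ) be the probability that the baseline count is 4 or fewer, s(λ) the probability that one reported follow-up count is 4 or fewer, and e(λ) the mean of r(X) over quarters reported as 4 or fewer. The subgroup rate in an arm is ∫ b s³ e dG / ∫ b s⁴ dG, where G is the distribution of λ. The ratio is no screening over screening. Under-reporting is binomial thinning of the four follow-up counts in one arm.

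**Results over the whole grid.**

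| Case | Five-period rule | Baseline rule | All participants |
|---|---|---|---|
| Arm affects nothing | 1.00 | 1.00 | 1.00 |
| No-screening arm under-reports by 20% | 1.17-1.21 steep, 1.10-1.14 middle, 1.04-1.06 shallow | 1.00 | 1.00 |
| Screening arm under-reports by 20% | 0.83-0.86, 0.88-0.91, 0.94-0.96 | 1.00 | 1.00 |
| No-screening arm truly has 20% fewer partners | 0.93-0.98 | 0.81-0.94 | 0.82-0.92 |

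At 10% under-reporting in the no-screening arm, the five-period rule gives 1.08-1.10, 1.05-1.06 and 1.02-1.03. A separate simulation (mean 6, shape 1.2, risk proportional to the square root of partners + 0.5) gave 1.04, 1.07 and 1.11 for 10%, 20% and 30% under-reporting in that arm, with the baseline rule again at 1.00.

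**Retention.** The five-period rule keeps 15-48% of participants and the baseline rule 34-67%. Of those who qualify at baseline, 29-56% would exceed 4 partners in a later period.

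**Precision, one setting (mean 6, shape 1, 912/2 = 456 per arm).** The five-period rule keeps 0.357×456 = 163 per arm. Subgroup rates of 0.0428, 0.0568 and 0.1069 per visit (steep, middle, shallow) give d = 163×4×rate = 28, 37 and 70 diagnoses per arm. The 95% CI factor exp(1.96√(2/d)) is 1.69 at d = 28 and 1.39 at d = 70. Without bias, the chance that the upper limit falls below 1.25 is Φ(ln 1.25/√(2/d) − 1.96) = 13%, 16% and 26%. Under the baseline rule d is 77-126, the factor is 1.37-1.28 and the chance is 28-43%.

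**Visit window.** Protocol Table 2 asks at follow-up about partners since the preceding visit, and 11.3.4 lets visits fall one week early to 6 weeks late. At a constant rate of new partners, 4 in 13 weeks becomes 4×19/13 = 5.8 in 19 weeks. This adds error in both arms; it is an arm bias only if visit timing differs by arm.

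**The case against.** Nothing in the documents shows that arm changes partner numbers. The certificate-of-health argument in protocol 3 concerns safety measures such as condoms, and Table 3 speaks only of risk behaviour in general. A reader might infer from these passages that the subgroup result will be biased, or biased in a known direction. They do not support that. What they establish is a comparison left unprotected, and every distribution and percentage shift above is assumed.

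The definition also follows a stated purpose. Protocol 2 is about people with persistently few partners, and a single baseline count captures that less well. The two rules answer different questions, and which one leads is partly a choice of estimand. This stands, and it is why the five-period version should be kept.

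The consequence is limited too. The subgroup is absent from the listed objectives and endpoints. Protocol 2 calls it a secondary outcome and 11.3.2 a sensitivity analysis. Use of the 1.25 rule is inferred, not stated. In the setting worked above, the interval factor of 1.39-1.69 exceeds the assumed shifts, and neither rule has enough events for a confirmatory reading. In the per-protocol set the attendance point is restrained, because SAP Table 1 excludes anyone with fewer than three scheduled follow-up visits with results; the intention-to-treat set requires only one follow-up visit.

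None of this makes the five-period comparison a randomised one.

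**Conclusion.** The concern holds as a structural, conditional weakness of an exploratory subgroup. If arm affects actual or reported partner numbers, the five-period rate ratio mixes selection with the effect of screening. If it affects neither, there is no bias from this source. Size and direction are unknown.

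On the assumed inputs, a 20% reporting difference moves a true ratio of 1.00 to 1.04-1.21 or 0.83-0.96, depending on which arm under-reports. A real 20% fall in partners in the no-screening arm is mostly conditioned away. The result depends chiefly on how steeply infection risk rises with partner number; if risk does not depend on partners, the ratio stays at 1.00.

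A reader might go further and doubt the main conclusion of the trial. The documents do not support that: the primary analysis does not use partner counts, and the 912/1014 sample size does not depend on them.

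**What to change.** In SAP 7.1 and protocol 11.3.2:
- Define the main lower-risk subgroup as 4 or fewer partners in the 3 months before enrolment.
- Report the rate ratio with its 95% CI in both the lower- and higher-risk groups, labelled exploratory.
- Keep the five-period definition as a sensitivity analysis, with a caution that it conditions on behaviour after randomisation.
- Tabulate reported partners by arm and visit, so that readers can see whether the counts diverge.
- Note the mismatch between the follow-up question and a fixed 3-month period, but do not rescale the counts. Rescaling assumes partners accrue in proportion to time; four regular partners over 19 weeks would become 4×13/19 = 2.7.

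The cost is a few sentences and one table, with no new data. The drawback is that a baseline count is a noisier marker of persistently low risk. The retained sensitivity analysis covers that question.

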7.2. Other aspects

a. *Multiplicity*

As this is a study with a single primary efficacy endpoint, no multiplicity adjustments are needed.

b. *Missing data*

Visits with missing data on the diagnosis of Ng or Ct, will be excluded from the calculation of the incidence rate (excluded both from numerator and denominator).

8. Analysis of secondary objectives

8.1. To compare the antimicrobial exposure (ceftriaxone/azithromycin/doxycycline) in the screening and non-screening arms

A Poisson regression model (or a negative binomial regression model if there is overdispersion) with number of standard doses as dependent variable, arm and hospital as independent variables and log(time at risk) as offset will be fitted. Time at risk will be calculated from day of enrollment until end of follow-up.

8.2. To assess if not screening MSM on PrEP for Ng/Ct is non-inferior compared to screening in terms of the incidence rate of symptomatic Ng and Ct infections

In each arm, the incidence of symptomatic Ng plus Ct will be estimated together with 95% confidence interval. Estimates will be based on a Poisson regression model (or a negative binomial regression model if there is overdispersion) with number of symptomatic diagnoses as dependent variable, arm and hospital as independent variables and log(number of visits) as offset. This model will also provide an estimate of the log incidence rate ratio (no screening versus screening), together with 95% confidence interval. The 'no screening' arm is proven to be non-inferior if the upper limit of the 95% confidence interval is lower than log(1.25).

Visits with missing data on the diagnosis of Ng or Ct, will be excluded from the calculation of the incidence rate (excluded both from numerator and denominator).

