These considerations have resulted in the current proposal where we plan to conduct an individual level RCT to assess if 3x3 screening for Ng/Ct is associated with a reduced incidence of these infections after 12 months screening versus no screening. One of the secondary outcomes will be assessing the efficacy of screening in those with relatively lower risk behavior (defined as 4 or fewer partners per 3 month period; represented by the lower connectivity network in Figure 3).

We are aware that participants in the no-screening arm would not be receiving the standard of care prescribed according to the Belgian PrEP guidelines. These PrEP guidelines were however developed by the Belgian Research on AIDS and HIV Consortium (BREACH) and discussions within BREACH informed by local research have led to serious doubts about the merit of 3x3 Ng/Ct screening [4, 6, 12, 14, 25]. For the reasons outlined above, we are concerned that our current guidelines may even be doing more harm than good. As a result, the 2018 annual general meeting of BREACH endorsed an RCT to evaluate the benefits and harms of 3x3 screening in Belgium PrEP cohorts. This study is thus the product of local efforts to produce evidence to help establish what the best standard of care should be vis-à-vis screening for Ng and Ct in PrEP recipients.

Phase II - cessation of Ng/CT screening in MSM

If the GonoScreen Study finds that screening is not associated with a reduced incidence of Ng plus Ct infections, then a second phase of the study is foreseen (separate from the current study proposal). In this second phase, we will present the GonoScreen Study results to BREACH with the recommendation that we cease screening MSM (PrEP recipients and other MSM) whilst closely monitoring the impact this has on incident STIs in a yet to be agreed upon strategy.

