11.3.3 Secondary outcome analysis

- 1) We will compare the antimicrobial exposure (ceftriaxone/azithromycin/doxycycline) in the two arms. Antimicrobial exposure will be measured as number of standard doses per 1000 person-years based on standard WHO and ECDC methodology [41]. Data on all antimicrobials consumed will be collected at each study visit and will include antimicrobials consumed at other health facilities such as at participant's General Practitioner. A Poisson regression model with number of standard doses as dependent variable, arm as independent variable, log(time at risk) as offset and a random intercept for site will be fitted.
- 2) Incidence rate of symptomatic Ng and Ct. This information will be collected at all visits and will include episodes of symptomatic Ng and Ct diagnosed elsewhere as long as these were laboratory confirmed diagnoses – either based on molecular testing or in the case of Ng, culture. The analysis will be analogous to the analysis of the primary objective, but the endpoint is calculated using symptomatic infections only.
- 3) Incidence rate of syphilis. The European IUSTI case definition of a syphilis infection will be followed [51]. A Poisson regression model with number of incident syphilis infections as dependent variable, arm as independent variable, log(time at risk) as offset and a random intercept for site will be fitted.
- 4) Incidence rate of HIV. A Poisson regression model with incident HIV infection as dependent variable, arm as independent variable, log(time at risk) as offset and a random intercept for site will be fitted.
- 5) Economic impact of cessation of 3x3 screening in MSM in Belgium (see section 11.4)
- 6) Participants' perception/experience and preference for screening vs. no screening (see section 8.11, only for ITM subjects)

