2.2. Study objectives

Primary objective:

To assess if not screening MSM on PrEP for Ng/Ct is non-inferior compared to screening in terms of the incidence rate of these infections over a 12-month period.

Secondary objectives:

- 1) To compare the antimicrobial exposure (ceftriaxone/azithromycin/doxycycline) in the screening and non-screening arms
- 2) To assess if not screening MSM on PrEP for Ng/Ct is non-inferior compared to screening in terms of the incidence rate of symptomatic Ng and Ct infections
- 3) To assess the incidence of syphilis
- 4) To assess the incidence of HIV
- 5) To evaluate the economic impact of cessation of Ng/Ct screening in MSM
- 6) To explore PrEP users' perceptions towards STI screening (only for ITM subjects)

3. General analysis strategy

Scheduled visits that were performed out of window (cfr. protocol) are considered as unscheduled visits, with the corresponding scheduled visit considered as 'not done'.

4. Description of study population

The study population will be described overall and in each hospital separately.

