Interim analyses are planned at two time points: once 50% and 100% of all study recruits have passed their 6 month visit. For the first interim analysis, data is used of the first 507 enrolled participants (i.e. ordered by randomization date) until 6 months follow-up. For the second analysis, data is used of all enrolled participants until 6 months follow-up. The goal of the interim analyses (at both time points) is to estimate the incidence rate ratio of symptomatic Ng plus CT. Estimates will be based on a Poisson regression model (or a negative binomial regression model if there is overdispersion) with number of symptomatic diagnoses as dependent variable, arm and hospital as independent variables and log(number of visits) as offset. This model will provide estimates of the incidence rate in each arm and the incidence rate ratio (no screening versus screening), together with 95% confidence interval. Visits with missing data on the diagnosis of Ng or Ct, will be excluded from the calculation of the incidence rate (excluded both from numerator and denominator).

7. Analysis of main efficacy outcomes: Incidence of Ng plus Ct

In each arm, the incidence of Ng plus Ct will be estimated together with 95% confidence interval. Estimates will be based on a Poisson regression model (or a negative binomial regression model if there is overdispersion) with number of diagnoses as dependent variable, arm and hospital as independent variables, and log(number of visits) as offset. This model will also provide an estimate of the log incidence rate ratio (no screening versus screening), together with 95% confidence interval. The 'no screening' arm is proven to be non-inferior if the upper limit of the 95% confidence interval is lower than $\log(1.25)$.

Visits with missing data on the diagnosis of Ng or Ct, will be excluded from the calculation of the incidence rate (excluded both from numerator and denominator).

In a sensitivity analysis, the numerator of the primary endpoint will only include diagnoses if there was a negative test result at the prior visit.

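### SAP 8.2 lets symptomatic non-inferiority be declared proven whatever the primary result; the multiplicity waiver in SAP 7.2 covers only the primary test

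*SAP*

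**What the plan says.** SAP 7.2(a), within the section on the main efficacy outcome, gives the whole position on multiplicity: "As this is a study with a single primary efficacy endpoint, no multiplicity adjustments are needed".

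The primary decision rule in SAP section 7 reads "The 'no screening' arm is proven to be non-inferior if the upper limit of the 95% confidence interval is lower than" log(1.25). SAP 8.2 repeats the sentence for symptomatic Ng plus Ct with the same interval and margin. This matches secondary objective 2 in SAP 2.2, which is framed as a non-inferiority comparison of symptomatic infections. Protocol 11.3.3 treats the endpoint the same way: "The analysis will be analogous to the analysis of the primary objective, but the endpoint is calculated using symptomatic infections only".

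The lower-risk subgroup has no decision sentence of its own. SAP 7.1 says "The analysis will be analogous to the analysis of the primary objective, but restricted to participants with lower-risk behavior". Its label varies. Protocol section 2 says "One of the secondary outcomes will be assessing the efficacy of screening in those with relatively lower risk behavior". Protocol 11.3.2, under a subgroup heading, says "We will conduct a prespecified sensitivity analysis to assess the incidence of Ng plus Ct in screening vs. non-screening arms". SAP 7.1 calls it a subgroup analysis.

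Neither document sets a testing order, a condition on the primary result, a split of alpha, or a statement that the symptomatic or subgroup results are descriptive.

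**The concern.** A single primary endpoint is a sound reason for not adjusting the primary test. It is no reason for leaving a second declaration of proof uncontrolled. Unadjusted secondary endpoints are common, but they are usually read as supportive. Here the plan uses the primary's word, interval and margin for a secondary endpoint.

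Followed literally, the plan lets the report say that stopping screening failed the 1.25 criterion for all infections but is proven non-inferior for symptomatic ones. Symptomatic disease is the main safety concern in Protocol 10.1.1, so readers would give that statement weight. The trial is sized for the primary test alone.

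**Working it through.** **1. Reproduce the design (Protocol 11.1).** Baseline mix 79/18/3%; mean diagnoses per visit 0.15, 0.28 and 0.34.

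- Mean per visit: 0.79 × 0.15 + 0.18 × 0.28 + 0.03 × 0.34 = 0.1791. Over four visits: 0.716 (stated 0.72).
- Mean visits: 0.95 × 4 + 0.05 × 3 = 3.95.
- Expected diagnoses per arm with 912 analysed: 456 × 3.95 × 0.1791 = 322.6.
- SE of the log ratio: √(2/322.6) = 0.0787.
- Power at a true ratio of 1: Φ(log(1.25)/0.0787 − 1.96) = 80.9%. Simulating the protocol's own model gives 80.3% (stated 80%).
- 912/0.90 = 1013.3, rounded up to 1014, as stated.

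The sample size therefore matches one test at one-sided 2.5%.

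**2. Error with two ungated declarations.** Each rule has a 2.5% chance of a false pass when its true ratio is exactly 1.25. Symptomatic diagnoses are a subset of all diagnoses, so for Poisson counts the two test statistics have correlation √f, where f is the symptomatic share. The documents do not give f, so 5% to 40% is assumed. The chance of at least one false declaration is 1 − P(Z₁ < 1.96 and Z₂ < 1.96) under a bivariate normal.

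| Assumed share f | Correlation √f | At least one false declaration | Primary fails, symptomatic declared |
|---|---|---|---|
| 5% | 0.22 | 4.8% | 2.3% |
| 10% | 0.32 | 4.8% | 2.3% |
| 20% | 0.45 | 4.6% | 2.1% |
| 30% | 0.55 | 4.5% | 2.0% |
| 40% | 0.63 | 4.3% | 1.8% |

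The last column is the third minus 2.5%. The ceiling, for independent tests, is 1 − 0.975² = 4.9%. If the symptomatic declaration is allowed only after the primary passes, the third column falls to 2.5% and the last to zero.

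**3. What the symptomatic test can deliver.** Assume 10% to 20% symptomatic diagnoses per person-year; Protocol 10.1.1 cites over 10% per year for symptomatic urethral Ng alone. With 456 per arm, SE = √(2/(rate × 456)), and power at a true ratio of 1 is Φ(log(1.25)/SE − 1.96). The largest estimate that passes is 1.25/exp(1.96 × SE).

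| Rate per person-year | Diagnoses per arm | SE | Power | Largest passing estimate |
|---|---|---|---|---|
| 10% | 45.6 | 0.209 | 19% | 0.83 |
| 15% | 68.4 | 0.171 | 26% | 0.89 |
| 20% | 91.2 | 0.148 | 33% | 0.94 |

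**4. Away from the boundary.** If the true symptomatic ratio were 1.5 at 15% per year, SE = √(1/68.4 + 1/102.6) = 0.156. The chance of a false symptomatic pass is Φ(log(1.25/1.5)/0.156 − 1.96), about 0.1%. The figures in step 2 are therefore the worst case.

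**The case against.** The SAP 7.2 sentence sits in the section on the main outcome and is right there: nothing else shares the primary's alpha. That stands. The gap is in SAP 8.2.

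The excess error is about two percentage points and arises in full only when both true ratios are at 1.25. That also stands. Moreover, a symptomatic declaration after a missed primary need not be false, since the primary misses 20% of the time by design when the arms are equal.

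The best argument against strict gating comes from Protocol 4.3.1. The primary count may include unresolved infections in the no-screening arm only, which biases against non-inferiority, although the protocol thinks this unlikely. If the primary failed for that reason, a fixed sequence would also give up the symptomatic declaration. This is a good reason to allow a descriptive alternative and always to report the estimate. It does not justify an unconditional declaration.

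A reader might infer that a secondary success would be used to recommend stopping screening. The documents point the other way. The phase II text in Protocol section 2 rests the recommendation on Ng plus Ct incidence. Protocol 11.4 makes the cost-saving analysis conditional on non-inferiority in the primary outcome and continues from there to the recommendation. These passages limit the likely consequence but do not gate the claim in SAP 8.2.

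**Conclusion.** The gap is real and modest. SAP 8.2 adds a second, ungated declaration of proof. The chance of at least one false declaration is about 4.3% to 4.8% against 2.5%, if both true ratios equal 1.25 and 5% to 40% of diagnoses are symptomatic. That a symptomatic claim can follow a failed primary does not depend on the assumed share.

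Three stronger readings are not supported:

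- The primary's own error is not inflated. The interim analyses in SAP section 6 estimate the symptomatic ratio and declare no non-inferiority.
- A reader might count the lower-risk subgroup as a third confirmatory test and quote a higher error rate. SAP 7.1 only calls that analysis analogous and does not restate the rule, so such a figure is not established. The wording should still be closed off.
- The antimicrobial, syphilis and HIV analyses (SAP 8.1, 8.3, 8.4) contain no decision rule and need no relabelling on this account.

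**What to change.** 1. **SAP 7.2(a):** limit the sentence to the primary analysis.
2. **SAP 8.2:** choose one of two forms. Either the non-inferiority rule for symptomatic infections is applied only if the primary analysis has met its criterion, at the same confidence level; or the declaration is removed and the symptomatic rate ratio with its 95% confidence interval is reported as supportive. In both forms the estimate and interval are reported whatever the primary shows.
3. **SAP 7.1:** state that the lower-risk analysis gives an estimate and 95% confidence interval with no declaration of proof. Call it a subgroup analysis in Protocol section 2 and Protocol 11.3.2 as well.

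The cost is a few sentences, with no change to sample size, data collection, or the alpha and power of the primary test. What is given up is a stand-alone symptomatic declaration after a failed primary. With about 19% to 33% power under the rates assumed above, that is a small loss.
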